3.5 Drug Metabolism and Pharmacokinetics

Plasma levels of LSALT peptide were measured post-intravenous dosing of 100, 250 and 450 mg/kg in rats. Terminal elimination half-lives of 0.66 – 1.17 hr and MRT_{obs} values of 0.58 – 0.85 hr were observed for LSALT peptide. The AUC_{0- ∞} was linear and close to proportional with dose.

LSALT peptide is stable in human plasma for up to 90 minutes with no detectable metabolic/proteolytic fragments as measured by mass spectrometry. LSALT peptide is undetectable in whole blood in the absence of phosphoric acid due to red or white blood cell binding. In human whole blood, 90% or more of the LSALT peptide is contained within the cellular compartment. LSALT peptide however is compatible with blood and does not induce red blood cell hemolysis. Work is ongoing to identify LSALT peptide volume of distribution, tissue biodistribution, and excretion.

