8.2. Derived PK Parameters

SAD:

The following plasma PK parameters will be derived for the SAD study portion.

Parameter	Definition	Method of Determination
AUC ₀₋₂₄	Area under the plasma concentration-time curve, from time 0 to 24 hours.	Linear trapezoidal method
AUC ₀₋₁₂	Area under the plasma concentration-time curve, from time 0 to 12 hours.	Linear trapezoidal method
AUC _{0-t}	Area under the plasma concentration-time curve, from time 0 to the last measurable concentration.	Linear trapezoidal method
AUC _{0-inf}	Area under the plasma concentration-time curve, from time 0 extrapolated to infinity.	AUC _{0-t} + C _{last} /λ _z , where C _{last} is the last measurable concentration.
%AUC _{exp}	Percentage of AUC _{0-inf} due to extrapolation from the time of last concentration to infinity.	(1 - AUC _{0-t} /AUC _{0-inf}) * 100

This document is confidential.

Parameter	Definition	Method of Determination
C_{max}	Maximum observed plasma concentration.	Observed directly from data
T_{max}	Time to reach C_{max} . If the maximum value occurs at more than 1 timepoint, T_{max} is defined as the first timepoint with this value.	Observed directly from data
$t_{1/2}$	Apparent first-order terminal elimination half-life.	$\ln(2)/\lambda_z$
λ_z	Apparent first-order terminal elimination rate constant.	Estimated by linear regression of the terminal elimination phase of the log-linear drug concentration-time curve
Cl/F	Apparent total body clearance.	Estimated as Dose/AUC _{0-inf}
V_z/F	Apparent volume of distribution.	Estimated as Dose/(\mathbf{\lambda}_z \times AUC_{0-inf})

MAD:

The following plasma PK parameters will be derived for the MAD study portion, for Day 1 and Day 3.

Parameter	Definition	Method of Determination
AUC_{0-24}	Area under the plasma concentration-time curve, from time 0 to 24 hours. (Day 1)	Linear trapezoidal method
AUC_{0-12}	Area under the plasma concentration-time curve, from time 0 to 12 hours. (Day 1)	Linear trapezoidal method
AUC_{0-tau}	Area under the curve over a dosing interval at steady state (Day 3 only)	Linear trapezoidal method
AUC_{0-t}	Area under the plasma concentration-time curve, from time 0 to the last measurable concentration.	Linear trapezoidal method
AUC_{0-inf}	Area under the plasma concentration-time curve, from time 0 extrapolated to infinity.	$AUC_{0-t} + C_{last}/\lambda_z$, where C_{last} is the last measurable concentration.

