8.3. Summary of PK Variables

Concentration:

Plasma concentrations will be listed and summarized, by nominal sampling time, and cohort/actual treatment. Concentrations below the quantification limit (BLQ) will be set to zero in summary tables. BLQ will be displayed in listings.

Individual subject and mean \pm SD profiles of the plasma concentration-time data will be plotted by dose level/cohort using actual and nominal times, respectively. These profiles will be presented on both linear-linear and log-linear scales.

This document is confidential.

For individual plots the BLQ values that occur in a profile before the first measurable concentration will be set to zero, and the BLQ values that occur after first measurable concentration will be set to missing. For mean plots, BLQ will be set to zero.

Parameters:

Plasma PK parameters will be listed and summarized descriptively by dose level/cohort.

For derivation of plasma pharmacokinetic parameters, the BLQ values that occur in a profile before the first measurable concentration will be set to zero. The BLQ values that occur after first measurable concentration will be set to missing.

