8.4. Assessment of Dose Proportionality

SAD and MAD:

For the SAD and MAD portions, an exploratory assessment of dose proportionality will be undertaken for the PK parameters AUC_{0-t} , $AUC_{0-\infty}$, and C_{max} (SAD) and AUC_{0-24} (Day 1), C_{max} , AUC_{0-t} , $AUC_{0-\infty}$ (Days 1 and 3) and AUC_{0-tau} (Day 3) (MAD). The power model will be used, and will include the PK parameter as the response variable and dose (mg) as the explanatory variable. For this model, the variable dose will be treated as a continuous variable. Cohorts that will be considered for the analysis include LSALT dose levels ≥ 1.0 mg (where a minimum of three different dose levels are required in order to conduct the analysis). The form of the model is as follows:

$$\text{PK Parameter} = e^{\alpha} \times \text{Dose}^{\beta} \times e^{\epsilon}, \quad \text{where Dose} \geq 0, \text{ and } e^{\epsilon} \text{ represents the associated error.}$$

Thus, perfect dose proportionality is met when $\beta=1$ (ignoring error). This becomes a linear relationship following a natural-log transformation, to which a linear regression will be fit by ordinary least squares (OLS):

$$\ln(\text{PK Parameter}) = \alpha + \beta \times \ln(\text{Dose}) + \epsilon, \quad \text{where Dose} > 0, \text{ and } \epsilon \text{ represents the associated error.}$$

The estimate of β together with a 90% confidence interval (CI) will be provided (for each PK parameter model), and this will be used to quantify dose proportionality. According to Hummel et al. (2009), the following criterion may be used for exploratory dose proportionality evaluations: If the (two-sided) 90% CI for β is wholly contained within the interval, $[1+\ln(0.5)/\ln(p), 1+\ln(2)/\ln(p)]$, then dose proportionality is suggested across the investigated dose range. Here, p is defined as the ratio of the highest to lowest dose. This interval criterion will be reported along with the corresponding 90% CI estimate for β (presented to three decimal places).

The SAS code for the analysis model will follow the format given below (using the Mixed procedure to fit the linear regression). The input variables (or datasets) are depicted in slanted red text and have been given generic names.

```
proc mixed data=dataset order=data;
  model ln_pk_parameter = ln_dose / solution;
  estimate 'Beta Estimate' ln_dose 1 / cl alpha=0.1;
  ods output estimates = estimates;
run;
```

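### SAP 8.3 sets trailing BLQ values to missing and SAP 8.2 gives AUC0-12, AUC0-24 and AUC0-tau no extrapolation term, so as written these areas end at the last measurable sample, short of the interval they name

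*SAP*

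**What the plan says.** SAP 8.3 has two BLQ conventions. In concentration tables, "Concentrations below the quantification limit (BLQ) will be set to zero in summary tables". Parameters are treated differently: a BLQ result ahead of the first quantifiable one counts as zero, but from then on "the BLQ values that occur after first measurable concentration will be set to missing".

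SAP 8.2 defines AUC0-24 as "Area under the plasma concentration-time curve, from time 0 to 24 hours". AUC0-12 is defined in the same way to 12 h, and AUC0-tau covers the dosing interval on MAD Day 3. The only method given for all three is the linear trapezoid. AUC0-t, which ends at the last measurable concentration, is a separate row of the same tables. The term Clast/lambda_z appears for AUC0-inf alone. SAP 6.3 rules out imputation unless specified, and SAP 14 names the PK software but no partial-area setting.

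In SAP 8.4, "an exploratory assessment of dose proportionality will be undertaken for the PK parameters", and for the MAD part the list includes AUC0-24 (Day 1) and AUC0-tau (Day 3). RAUC in SAP 8.2 is built from AUC0-12 or AUC0-24.

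The only half-life in the documents is from rats (Protocol 3.5): "Terminal elimination half-lives of 0.66 – 1.17 hr".

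**The concern.** A trapezoid needs a value at or beyond the end of its interval. If every sample after Tlast is BLQ and therefore missing, nothing is left between Tlast and 12 h, 24 h or tau. Under the stated rules the area stops at Tlast. A row labelled AUC0-24 then holds AUC0-t, contrary to its own definition.

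A fixed-interval AUC is meant not to depend on assay sensitivity. Ended at Tlast, it is biased low by an amount set by the LLOQ and the sampling times. Because Tlast can come earlier at lower doses, the bias can differ by dose and push the dose-proportionality slope upwards. The parameters affected serve the secondary PK objective, and Protocol 3.8 says the third MAD cohort was added to obtain more PK data.

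**Working it through.** The documents give no figure to reproduce, so this is a model check.

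**Inputs from the documents.** The infusion lasts 2 h (Protocol 10.1.6). The rat half-lives are 0.66 and 1.17 h. MAD doses are 1, 2.5 and 5 mg (Protocol 7.2.2). The protocol MAD sampling times run from 15 min to 3 h after onset, then 24 h (Protocol 7.2.5). The SAP 8.1 times are 0.25, 0.5, 0.75, 1, 2, 4, 6, 8 and 12 h after the end of infusion, then 24 h.

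**Assumptions.** One compartment; human half-life equal to the rat values; LLOQ varied.

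**Formulae.** Let k = ln2/half-life.
- The concentration s hours after the end of infusion is exp(-ks) of its end-of-infusion value.
- The share of AUC0-inf lying after time T (from onset, T ≥ 2 h) is F(T) = [(1 - exp(-2k))/(2k)] × exp(-k(T - 2)). At these half-lives AUC0-24 and AUC0-inf are practically equal.

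**Is trailing BLQ likely?** At 24 h from onset the concentration is exp(-22k) of the end-of-infusion value: 9e-11 at 0.66 h and 2.2e-6 at 1.17 h. On these values it would be.

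**Protocol MAD times, Tlast = 3 h.**
- 0.66 h: k = 1.050; F(3) = 0.418 × 0.350 = 0.146.
- 1.17 h: k = 0.592; F(3) = 0.586 × 0.553 = 0.324.

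Linear trapezoids to 3 h give 0.858 and 0.677 of the true AUC0-24, so it is understated by 14% and 32%. Adding the area from Tlast to 24 h gives 0.858 + 0.146 = 1.004 and 0.677 + 0.324 = 1.001.

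**SAP 8.1 times, exact area lost after Tlast.** The LLOQ is a percentage of the 1 mg end-of-infusion concentration. Each pair of figures is for half-lives of 0.66 h / 1.17 h.

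| LLOQ | Lost at 1 mg | Lost at 5 mg | Shift in beta |
|---|---|---|---|
| 0.1% | 0.1% / 0.5% | 0.01% / 0.05% | 0.000 / 0.003 |
| 1% | 0.6% / 1.7% | 0.6% / 0.5% | 0.000 / 0.008 |
| 5% | 5.1% / 5.5% | 0.6% / 1.7% | 0.027 / 0.025 |
| 10% | 5.1% / 17.9% | 5.1% / 1.7% | 0.000 / 0.114 |
| 25% | 14.6% / 17.9% | 5.1% / 5.5% | 0.068 / 0.083 |

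The largest shift in full (1.17 h, LLOQ 10%):
- Tlast is 4, 6 and 8 h from onset at 1, 2.5 and 5 mg, and the losses are 17.9%, 5.5% and 1.7%.
- ln(1 - loss) is -0.198, -0.056 and -0.017.
- ln(dose) is 0, 0.916 and 1.609, with mean 0.842 and sum of squares 1.303.
- The slope is 0.149/1.303 = 0.114.

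Using linear trapezoids on the same points, the ratios to truth are 0.667, 0.806 and 0.848. Their logs are -0.405, -0.216 and -0.165, and the slope is 0.198/1.303 = 0.15. It is larger because these times include no sample during infusion, so the trapezoid total is smaller and the lost tail is a bigger share of it.

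**Criterion.** With p = 5, the interval is 1 ± ln2/ln5 = 0.569 to 1.431, a half-width of 0.431.

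**Would zero-setting repair it?** On the protocol MAD times, a zero at 24 h adds a triangle of base 21 h. As a share of the true area this is 10.5 × k × F(3) = 1.61 (0.66 h) and 2.02 (1.17 h). AUC0-24 becomes 0.858 + 1.61 = 2.47 and 0.677 + 2.02 = 2.69 times the true value.

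**The case against.** The strongest reply is that truncation is not the declared intention. SAP 8.2 defines AUC0-24 as reaching 24 h, lists AUC0-t separately, already estimates lambda_z, and nowhere forbids extrapolating within the interval. The pharmacokineticist may do so by default. That stands as far as it goes: a reader might infer that truncated values will certainly be reported, and the documents do not establish that. But the extrapolation term is written for one parameter and withheld from three others in the same table, and no software setting fills the gap.

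A reader might also infer that every BLQ value set to missing does harm. An embedded one does not: its measurable neighbours bridge it, and the interval is still covered.

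The 14% to 32% depends on the protocol MAD times, which SAP 8.1 contradicts. If Tlast is 3 h at every dose and on both days, the loss at a given half-life is a common factor and cancels in beta and in RAUC. So these losses do not show that dose proportionality or accumulation would be misjudged. That stands.

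On the SAP times a sensitive assay makes the loss trivial. The larger losses need an LLOQ of roughly 5% or more of the 1 mg end-of-infusion concentration. AUC0-t and AUC0-inf are also modelled, and %AUCexp would show the missing share wherever lambda_z is estimable. This limits the damage, but leaves the fixed-interval rows mislabelled.

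A far larger distortion can be built. With a 3 h half-life, if the 24 h sample is BLQ at 1 mg but measurable at 2.5 and 5 mg, beta is 2.07 on the protocol times. That half-life is outside the only documented range, and part of the effect comes from the long 3 to 24 h linear trapezoid at the higher doses, which is a separate matter. It is not counted here.

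**Conclusion.** The point holds for trailing BLQ values. As written, AUC0-12, AUC0-24 and AUC0-tau collapse to AUC0-t whenever Tlast precedes the interval end.

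Under the model, AUC0-24 is about 14% (half-life 0.66 h) to 32% (1.17 h) too low on the protocol MAD times. On the SAP 8.1 times the loss is under 1% to about 18% at 1 mg. Beta shifts by 0 to about 0.11 on exact areas, or up to about 0.15 with trapezoids among the settings tried. Both are well inside the 0.431 half-width of a criterion that SAP 8.4 calls exploratory.

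These sizes rest on a one-compartment model, on rat half-lives standing in for human ones, and on assumed LLOQs. Which size applies cannot be settled until the protocol and SAP MAD schedules are reconciled. The primary safety analysis is not affected.

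**What to change.** In SAP 8.2 and 8.3:

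- When Tlast precedes the interval end T_end and lambda_z is estimable (at least three points, as SAP 8.2 already requires), add (Clast/lambda_z) × (1 - exp(-lambda_z × (T_end - Tlast))) to AUC0-12, AUC0-24 and AUC0-tau, and report the percentage extrapolated.
- Where lambda_z is not estimable, report the parameter as not estimable. Do not set the trailing BLQ value to zero.
- Flag affected profiles in AUC0-24, AUC0-tau and RAUC.
- Keep the existing BLQ rule for AUC0-t and lambda_z.
- Reconcile the MAD sampling times in Protocol 7.2.5 and SAP 8.1.

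The cost is SAP wording and a software setting, with no new samples. The downside is small: part of the area is extrapolated. On the protocol MAD times lambda_z would rest on about 1 h of post-infusion data (1/1.17 = 0.9 to 1/0.66 = 1.5 half-lives), which is why the percentage should be shown.

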8.4. Assessment of Dose Proportionality

SAD and MAD:

For the SAD and MAD portions, an exploratory assessment of dose proportionality will be undertaken for the PK parameters AUC_{0-t} , $AUC_{0-\infty}$, and C_{max} (SAD) and AUC_{0-24} (Day 1), C_{max} , AUC_{0-t} , $AUC_{0-\infty}$ (Days 1 and 3) and AUC_{0-tau} (Day 3) (MAD). The power model will be used, and will include the PK parameter as the response variable and dose (mg) as the explanatory variable. For this model, the variable dose will be treated as a continuous variable. Cohorts that will be considered for the analysis include LSALT dose levels ≥ 1.0 mg (where a minimum of three different dose levels are required in order to conduct the analysis). The form of the model is as follows:

$$\text{PK Parameter} = e^{\alpha} \times \text{Dose}^{\beta} \times e^{\epsilon}, \quad \text{where Dose} \geq 0, \text{ and } e^{\epsilon} \text{ represents the associated error.}$$

Thus, perfect dose proportionality is met when $\beta=1$ (ignoring error). This becomes a linear relationship following a natural-log transformation, to which a linear regression will be fit by ordinary least squares (OLS):

$$\ln(\text{PK Parameter}) = \alpha + \beta \times \ln(\text{Dose}) + \epsilon, \quad \text{where Dose} > 0, \text{ and } \epsilon \text{ represents the associated error.}$$

The estimate of β together with a 90% confidence interval (CI) will be provided (for each PK parameter model), and this will be used to quantify dose proportionality. According to Hummel et al. (2009), the following criterion may be used for exploratory dose proportionality evaluations: If the (two-sided) 90% CI for β is wholly contained within the interval, $[1+\ln(0.5)/\ln(p), 1+\ln(2)/\ln(p)]$, then dose proportionality is suggested across the investigated dose range. Here, p is defined as the ratio of the highest to lowest dose. This interval criterion will be reported along with the corresponding 90% CI estimate for β (presented to three decimal places).

The SAS code for the analysis model will follow the format given below (using the Mixed procedure to fit the linear regression). The input variables (or datasets) are depicted in slanted red text and have been given generic names.

```
proc mixed data=dataset order=data;
  model ln_pk_parameter = ln_dose / solution;
  estimate 'Beta Estimate' ln_dose 1 / cl alpha=0.1;
  ods output estimates = estimates;
run;
```

The PK parameter values estimated from the power model will be plotted against dose. This plot will also include individual subject values \pm SD (separately by dose level).

This document is confidential.

9. Anti Drug Antibodies

Analysis of anti drug antibody data is outside the scope of this SAP. The sample collection dates and times will be listed.

This document is confidential.

10. Safety

Summaries of safety and tolerability data will be based on the Safety Population.

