7.2.5 MAD Study Procedures

- **Day -29. Pretreatment Evaluation and Randomization.** 29 days prior to study initiation, enrolled participants will undergo informed consent, followed by a complete history and physical examination (including body weight and height) vital signs (seated), alcohol breath test, drugs of abuse test, baseline fasting laboratory studies (CBC, clinical chemistry) including coagulation profile (INR and PTT), urinalysis, 12-lead, electrocardiogram (supine) and chest x-ray (single PA view). Women of child-bearing age will have a β -hCG to rule out pregnancy. Participants will then be randomized.
- **Day -1.** Admission to unit. Participants will undergo a clinical evaluation including complete vital signs and physical examination, 12-lead electrocardiogram (supine), drugs of abuse and alcohol breath test, urinalyses, 25 ml of blood drawn for safety laboratory investigations including CBC, clinical chemistries, urinalysis and women of child-bearing age will have a urine pregnancy test to rule out pregnancy.
- **Day 1.** Participants will undergo clinical evaluation including vital signs. 5 ml of blood will be drawn at 30 minutes prior to LSALT peptide infusion for baseline PK measurements. LSALT peptide infusion will begin and run over 2 hours. 5 ml of blood will be drawn at 15, 30, 45 60, 75, 90, 105, 120, 125, 130, 135, 140 minutes, and 3 hours from the onset of the LSALT infusion.

- **Day 2.** Participants will undergo a clinical evaluation, including vital signs, a brief history and symptom directed physical exam. 25 ml of blood will be drawn for laboratory investigations, including CBC, clinical chemistries and coagulation profile (INR and PTT), urinalysis and 24 hour PK sample (from the onset of the first LSALT infusion). An ECG will also be completed. If the participant shows no adverse events, they will receive the second dose of the LSALT peptide.
- **Day 3.** Participants will undergo a clinical evaluation, including vital signs, a brief history and a symptom directed physical exam. If the participant shows no adverse events, they will receive the third dose of the LSALT peptide. 5 ml of blood will be drawn at 15, 30, 45 60, 75, 90, 105, 120, 125, 130, 135, 140 minutes, and 3 hours from the onset of the LSALT infusion.

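### SAP 8.4 tests AUC0-t for dose proportionality although its end point can move with dose: the slope is biased upward, modestly on most of the planned grids and severely only under specific conditions on the protocol's MAD grid

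*SAP*

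**What the plan says.** SAP 8.2 defines AUC0-t as "Area under the plasma concentration-time curve, from time 0 to the last measurable concentration", computed by the "Linear trapezoidal method". For parameter derivation, SAP 8.3 adds that "the BLQ values that occur after first measurable concentration will be set to missing". The curve therefore ends at the last quantifiable sample, wherever that falls for a given participant.

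SAP 8.4 states that "an exploratory assessment of dose proportionality will be undertaken for the PK parameters", AUC0-t among them, and regresses the log of each PK parameter on log dose. The slope estimate "together with a 90% confidence interval (CI) will be provided", and if that interval lies inside limits set by the dose ratio, "then dose proportionality is suggested across the investigated dose range". The table shells in SAP 16 turn this into a Yes/No column for each parameter, AUC0-t included. No common integration window is specified, and no summary of last measurable time by dose.

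The MAD sampling times differ between the documents. Protocol 7.2.5 ends its dense sampling with "140 minutes, and 3 hours from the onset of the LSALT infusion", and the next sample is 24 h from the onset of that infusion. (On Day 3 the next sample is 72 h from the first onset, which is again 24 h after the third.) SAP 8.1 instead samples MAD participants from 15 minutes to 12 h after the end of infusion, and then at 24 h.

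**The concern.** A slope test of proportionality assumes that the response is the same quantity at every dose. AUC0-t is not, if the last measurable time rises with dose: the 5 mg value then covers a longer stretch of the curve than the 1 mg value. For a proportional drug this error goes one way, towards a slope above 1.

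A technical No in the AUC0-t row could be read as exposure rising faster than dose. The third MAD cohort was proposed to obtain more PK data (Protocol 3.8), so its PK summaries will be looked at closely.

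**Working it through.** The plan gives no power, sample-size or numerical limit for this analysis, so there is no figure to reproduce.

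**Inputs from the documents.** Doses 1, 2.5 and 5 mg; 6 active participants per dose; 2 h infusion; linear trapezoid; trailing BLQ missing; rat half-life 0.66-1.17 h (Protocol 3.5).

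**Assumptions.** One compartment; true slope 1; half-lives of 2-6 h as well as the rat range; LLOQ at 0.5-30% of the 1 mg end-of-infusion level unless stated; CV 20-40%.

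**Limits.** p = 5/1 = 5 and ln 2/ln 5 = 0.431, so the limits are 1 ± 0.431 = 0.569 to 1.431.

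**Room left by the CI.** Log doses are 0, 0.916 and 1.609; their squared deviations sum to 1.303, or 7.82 for 18 participants. With t(0.95; 16) = 1.746 and SD = √ln(1+CV²), the half-width is 1.746 × SD/√7.82 = 0.124, 0.183 and 0.241 at CV 20, 30 and 40%. The point slope must then stay below about 1.31, 1.25 and 1.19.

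**SAD timetable grid, half-life 1.17 h, LLOQ 10%.** Last measurable times are 4, 6 and 8 h from onset. With the 1 mg end-of-infusion level as the unit, AUC0-t is 1.923, 5.805 and 12.220 (logs 0.654, 1.759, 2.503). Slope = (−0.842×0.654 + 0.074×1.759 + 0.767×2.503)/1.303 = 1.152. Cutting all doses at 4 h gives 1.000.

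**What 1.152 costs.** At CV 30% the standard error is 0.294/√7.82 = 0.105. The chance of meeting the criterion is about Φ((1.247−1.152)/0.105) = Φ(0.91) = 82%, against about 98% when the slope is unbiased.

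**Range on the SAD timetable grid and the SAP's MAD grid.**
- Rat half-lives: 1.00 to 1.15 for LLOQ up to 20%. Close to 30% it can go higher. For example, half-life 1.0 h and LLOQ 30% give last times 3, 4 and 6 h, AUCs 1.439, 4.535 and 10.633, and slope 1.243; the largest value found was 1.27.
- Half-lives of 2-6 h: at most about 1.30 (half-life 2 h, LLOQ 30%: last times 4, 8 and 10 h).
- In simulated trials on the SAP's MAD grid with CV 30%, half-life 1.17 h and LLOQ 35% of the 1 mg Cmax, the pass rate fell from 98% to 59%.

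**Protocol MAD grid, half-life 4 h, LLOQ 10%.** k = 0.1733 per hour.
- The 24 h level per mg is e^(−22k) = 0.0221. At 5 mg it is 0.110 (measurable); at 2.5 mg 0.055 (not). Last times are 3, 3 and 24 h.
- AUC0-3 is 1.976 per mg. The single chord from 3 to 24 h adds 21 × (0.841+0.022)/2 = 9.06 per mg, where the true area is (0.841−0.022)/k = 4.72.
- AUC0-t is therefore 1.976, 4.939 and 55.185 (logs 0.681, 1.597, 4.011). Slope = (−0.842×0.681 + 0.074×1.597 + 0.767×4.011)/1.303 = 2.013. A common 3 h window gives 1.000.
- At LLOQ 5% the last times are 3, 24 and 24 h and the slope is 2.11. At LLOQ 1% all doses are measurable at 24 h and the slope is 1.00.

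**When that happens.** The LLOQ must lie between e^(−22k) and 5e^(−22k) of the 1 mg end-of-infusion level: 0.6-3.1% at 3 h, 2.2-11% at 4 h, 7.9-39% at 6 h. At 1.17 h the band is about 0.0002-0.001%. At rat half-lives with LLOQ up to 30% the slope on this grid is 1.00.

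**Same case on the SAP's MAD grid (4 h, 10%).** The slope is 1.07 if the 24 h sample is timed from onset and 1.00 if from the end of infusion.

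**AUC0-inf in the severe case.** It crosses the same chord. Its slope is 1.55, 1.42 and 1.32 at half-lives of 2, 3 and 4 h.

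**A further SAD reading.** The Day 1 narrative in Protocol 7.1.4 times SAD samples from infusion start; the timetable footnote and SAP 8.1 time them from its end. On the narrative times the slope at rat half-lives stays near 1.12 for LLOQ up to 10% of Cmax, but reaches about 1.4 by 20% and 1.69 near 37%.

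**The case against.** The tempting stronger reading is that a proportional drug will be declared non-proportional, and grossly so in the MAD part. The documents do not support it.

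- The gross result needs the protocol's 3-24 h gap, a half-life several times the only documented value (or a slow terminal phase), and an LLOQ inside one five-fold band. Neither the LLOQ nor a human half-life is given. The SAP's own MAD grid keeps the point slope inside the limits.
- The assessment is exploratory. The rule says when proportionality is suggested; it does not declare the opposite, and no dosing decision in the documents rests on it.
- Cmax, AUC0-inf and, in the MAD part, AUC0-24 and AUC0-tau are modelled alongside. The percentage extrapolated, the last time used for the terminal slope and individual profiles are also reported, so a careful reader could spot truncation.

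All of this limits the size and consequence, and it stands. It does not remove the bias. The safeguards are incomplete: AUC0-inf shares the 3-24 h chord, and nothing tells the reader to check last measurable time before reading the Yes/No column.

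**Conclusion.** The mechanism is certain from the SAP's definitions; its size is not. For LLOQ of 0.5-30%, the SAD timetable grid and the SAP's MAD grid give a noise-free slope of about 1.00-1.15 in most rat half-life settings, and at most about 1.30 overall. That lies inside 0.569-1.431 but lowers the chance that the 90% CI meets the criterion. A slope of about 2.0-2.2 arises only on the protocol's MAD grid, at half-lives of about 3-6 h, with the LLOQ between the 24 h levels of the lowest and highest dose; simulated trials in such settings never met the criterion at CV 20-40%. These figures rest on a one-compartment model and on assumed LLOQ, half-life and CV. The point is worth acting on because the correction is nearly free, not because a false result is shown to be likely.

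**What to change.** In SAP 8.4, make the AUC on which the exploratory criterion is interpreted an AUC over one common window per study part: the longest scheduled time quantifiable at all dose levels, chosen by a rule fixed before unblinding. Keep AUC0-t as a descriptive parameter, report the last measurable time by dose, and state the LLOQ.

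Reconcile the MAD sampling times of Protocol 7.2.5 and SAP 8.1, and the SAD times within Protocol 7.1.4. If the 3-24 h gap applies, read AUC0-inf with the same caution.

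The cost is SAP wording and one partial-AUC setting; no new samples. In simulation the common window restored a mean slope of about 1.00 in the settings where AUC0-t failed on the protocol's MAD grid, with pass rates of 97-98% at CV 30%. With an LLOQ of 35-45% of the 1 mg Cmax, a slope of about 1.04-1.08 remains on that grid.

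The drawback is coverage. On the protocol's MAD grid the common window may be only 0-3 h, which holds about 36% of total AUC at a 3 h half-life and 20% at 6 h. It should be shown beside AUC0-inf and Cmax, not instead of them.
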